Medical information regarding **co-morbidities** will be ascertained at the screening visit and reviewed at the 4- and 12-month follow-up visits. **Arthritis and joint pain** will be assessed by self-report on a questionnaire. We will record **medication and supplement use** at screening and 4- and 12-month follow-up. Participants will also be asked to bring in medications and dietary supplements for a "brown bag" review. The medication form will specifically ask about the use of vitamin D-containing supplements, anti-inflammatory agents, protein supplements, and sex steroids or corticosteroids.

Statistical Power

We anticipate that, based on the vitamin D₃ supplement dose of 2000 IU/d, 25(OH)D concentrations will increase by an average of 14 ng/mL in the intervention group at 12-month follow-up. In preliminary data from 17 older individuals with vitamin D concentrations between 20 and 40 ng/mL, we found that a 1 ng/mL difference in 25(OH)D concentration was associated with a 0.0233 watts/kg of body weight difference in lower extremity muscle power for men and women combined. If this cross-sectional relationship holds for the intervention study, we would expect approximately a 0.33 watts/kg difference between the two groups at follow-up ($0.0233 \times 14 = 0.33$). However, due to the uncertainty of extending cross-sectional data to longitudinal follow-up and the potential for non-adherence, we have based the power on a difference in means

of a 10% relative change between the two groups; a magnitude that resulted in a clinically meaningful increase on the SPPB in a previous intervention trial.⁴⁷ The mean (SD) of lower extremity muscle power was 1.74 (0.382) watts/kg in our preliminary data; a 10% difference (0.174 watts/kg) corresponds to an effect size of 0.45. A sample size of 125 participants randomized in a 1:1 ratio stratified by gender and race will have >80% power to detect this difference using analysis of covariance (ANCOVA), adjusting for the baseline measure, based on a baseline mean of 1.7 watts/kg (SD=0.444) and a correlation between baseline and 12-month follow-up of 0.708 with a 0.05 two-sided significance level. Allowing for a 10% dropout rate, we will inflate the sample size to 136. We will also have sufficient power to detect a difference of 0.45 SD or greater in our secondary outcomes (**Table 3**).

Table 3. Differences detected with 80% power for secondary outcomes

Outcome measure	SD*	Detectable difference

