Short Physical Performance Battery score ³⁰	2.05	0.92
Timed Up and Go, sec ⁸²	5.40	2.43
20-m Gait Speed, m/sec ³¹	0.15	0.07
Lower extremity muscle strength, Nm ³¹	21.0	9.5
Postural Sway, mm ¹²²		
Mediolateral (ML) displacement	2.7	1.2
Anteroposterior (AP) displacement	3.9	1.8

*SD calculated assuming a correlation of 0.43 between baseline and follow-up measures.

For the muscle biopsy subsample, we have powered on a difference between the two groups of a relative increase in type II fibers of 25% or more. In our preliminary data in older adults with 25(OH)D concentrations <25 ng/mL treated with 2000 IU/d vitamin D₃ plus 1200 mg/d calcium (n=4) or calcium only (n=2), a 1 ng/mL increase in 25(OH)D concentration was associated with a 2.35% relative increase in type II fibers over 4 months. Assuming that 25(OH)D concentrations will increase by an average of 14 ng/mL in the intervention group, we

expect to see a relative increase in type II fibers of approximately 33%. To allow for the possibility that there may be some increase in the control group due to “drop in” by starting vitamin D supplements or changes in physical activity, a 25% difference between the two groups in the relative increase in type II fibers was selected. Two previously published vitamin D supplementation studies observed increases in type II fibers of 31-34%⁴⁸ and 202%.⁴⁹ Thus, the detectable 25% relative increase is in line with independent observations. A sample size of 16 in each group will have 80% power to detect a difference of 25% assuming that the common standard deviation is 23.7 (based on preliminary data of n=17 participants in a behavioral intervention with data on change in type II muscle fibers) using a two group t-test with a 0.05 two-sided significance level. Allowing for 10% drop out, we will inflate the sample size to 18 per group, for a total of 36 participants. However, up to 40 participants may be approached for a baseline muscle biopsy to allow for biopsy samples that yield insufficient muscle for analyses.

Statistical Analyses

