We will examine the distributions of all continuous outcomes of interest, and will transform them to approximate normality if the outcomes show a strong departure from normality as evidenced by examining Q-Q plots and performing the Shapiro-Wilk test. Outliers will be examined on the chosen scale (original or transformed) and may be set to missing if they are 3 or more interquartile ranges above the 75th percentile or below the 25th percentile. Plausible biologic values may be retained even if they are outliers. Implausible biologic values may be set to missing based on a review of health-related events (e.g., AEs related to pain, fractures, surgery) in the interval surrounding the collection of the measurements.

The primary outcome for this trial will be the 12-month measure of muscle power. For the muscle biopsy substudy, the primary outcome will be the change in type II muscle fibers over 4-months. Our primary statistical analyses will proceed on the “intent-to-treat” principle in which data from all randomized participants are used to test the primary hypotheses that compared to placebo, vitamin D₃ supplementation will result in increases in lower extremity muscle power and strength, and improvements in physical performance (expanded SPPB, TUG, and 20-m walk speed) and balance. Even if participants wish to discontinue the supplements, we will still attempt to follow them for outcomes in order to carry out intent-to-treat analysis at 12 months. Characteristics of the participants missing the 12-month follow-up outcomes will be compared to participants without missing data using chi-square tests and t-tests to determine if there are any differences with regard to intervention group, demographic characteristics, and baseline neuromuscular function outcomes. If a particular group exhibits markedly higher drop-out rates, we will attempt to identify baseline covariates that predict attrition. If such covariates can be identified, the analyses of outcome measures may need to be stratified according to these comparisons to decrease bias. We will use a mixed model with an unstructured covariance matrix to model after-treatment neuromuscular function outcomes between the two groups by time, with adjustment for

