For the muscle biopsy subsample (n=16 per group), primary analyses will proceed on the “intent-to-treat” principle in which data from all randomized participants are used in analyses. All participants who complete the 4-month muscle biopsy and on whom the muscle fiber testing can be completed will be included in the analytic sample. Even if participants wish to discontinue the supplements, we will still attempt to follow them for outcomes in order to do the intention-to-treat analysis at 4 months. Characteristics of the participants missing the 4-month follow-up outcomes will be compared to participants without missing data using chi-square tests and t-tests to determine if there are any differences with regard to intervention group, demographic characteristics, baseline physical performance, and baseline muscle fiber testing. Our primary statistical analyses will focus on testing the primary hypotheses that, compared to placebo, vitamin D supplementation will result in changes in skeletal muscle composition and physiology as quantified by: fiber-type composition and size; fiber force, shortening velocity, and power; NCAM+ myofibers; Runx1, Chrn γ , Scn5a, Myh3, Myog, and NCAM1 expression; SC number; VDR expression; and bioenergetic capacity. For our primary outcome of percent type II fibers we will use analysis of covariance (ANCOVA) to model differences in percent of type II fibers between the two groups, with adjustment for the baseline measure, age, gender, and race. Analysis of other continuous measures will also use the ANCOVA model to compare the groups adjusted for age, gender, and race. In secondary analyses, we will examine if the percent of participants who have a relative increase in type II fibers of 25% or more from baseline differs by intervention group using Fisher’s Exact Test, and in logistic regression models adjusted for age, gender, and race. Furthermore, we will explore if the relationship between vitamin D supplementation and neuromuscular function is mediated by change in muscle composition and physiology by including the variables described above as covariates in the ANCOVA model described above. If the relationship between vitamin D supplementation and power decreases by 10% or more, it will be considered evidence of partial mediation.

Human Subjects Protection

Subject Recruitment Methods

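### The 10% coefficient-change rule for partial mediation makes no allowance for sampling error, so with 16 per group it can label a variable that mediates nothing

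*Combined protocol and SAP*

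**What the plan says.** The rule closes the muscle biopsy paragraph of Statistical Analyses. Mediation is to be explored "by including the variables described above as covariates in the ANCOVA model described above", and then: "If the relationship between vitamin D supplementation and power decreases by 10% or more, it will be considered evidence of partial mediation". The ANCOVA adjusts for the baseline measure, age, gender and race. The paragraph sets the subsample at 16 per group.

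The candidate variables listed there come to about 15: fiber-type composition and size (2); fiber force, velocity and power (3); NCAM+ fibers (1); six gene-expression measures (6); satellite cell number, VDR expression and bioenergetic capacity (3). The plan does not say whether they enter one at a time or together, or which visit's leg power is the outcome.

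Earlier in the same section one biopsy variable is singled out: "For the muscle biopsy substudy, the primary outcome will be the change in type II muscle fibers over 4-months". The sizes used below come from Statistical Power: "a 10% difference (0.174 watts/kg) corresponds to an effect size of 0.45"; "we would expect approximately a 0.33 watts/kg difference between the two groups at follow-up"; "based on a baseline mean of 1.7 watts/kg (SD=0.444) and a correlation between baseline and 12-month follow-up of 0.708"; and, for the substudy, "80% power to detect a difference of 25% assuming that the common standard deviation is 23.7".

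**The concern.** The rule compares two point estimates and gives the result a label. Adding any covariate to a regression in 32 people moves the treatment coefficient somewhat, even when the covariate has nothing to do with the outcome. If that chance movement is commonly larger than 10% of the effect, the label carries little information about mechanism.

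The awkward case is close to the substudy's own hypothesis. Suppose vitamin D raises type II fibers as planned, but fibers have no bearing on power. The fiber variable is then strongly related to treatment arm, and adding it makes the treatment coefficient less stable. What is at stake is the mechanistic interpretation, which the Background gives as part of the reason for the trial. The primary comparisons are not affected.

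**Working it through.** **Reproducing the plan's figure.** Difference 25, SD 23.7, two-sided 0.05, two-group t-test: noncentral t power is 79.6% at 15 and 82.3% at 16 per group. The stated 16 per group is confirmed. The planned shift in type II fibers is 25/23.7 = 1.05 SD. The documents give no error rate for the 10% rule, so there is none to reproduce.

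**Threshold against noise.**
- ANCOVA residual SD of leg power = 0.444 × √(1 − 0.708²) = 0.314 W/kg.
- SE of the treatment effect at 16 per group = 0.314 × √(2/16) = 0.111 W/kg.
- Threshold at 0.174 W/kg: 0.1 × 0.174 = 0.0174, and 0.0174/0.111 = 0.16 SE.
- Threshold at 0.33 W/kg: 0.1 × 0.33 = 0.033, and 0.033/0.111 = 0.30 SE.

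**Simulation with no true mediation.** Follow-up power = 1.7 + 0.708 × (baseline − 1.7) + effect × arm + normal error with SD 0.3136. ANCOVA on arm, baseline, age, gender and race was fitted with and without the mediator(s). A label was counted when (total coefficient − adjusted coefficient)/total coefficient ≥ 0.10. There were 20,000 trials per cell at n=32. Each pair is for a true effect of 0.33 / 0.174 W/kg.

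| Added variable(s) | Falls ≥10% | Rises ≥10% | SD of coefficient change (W/kg) |
|---|---|---|---|
| One, unrelated | 7.8% / 17.7% | 8.4% / 17.4% | 0.024 |
| One, shifted 1.05 SD by treatment, no effect on power | 29.0% / 37.5% | 28.7% / 38.3% | 0.071 |
| Fifteen unrelated, mutually independent, entered jointly | 39.8% / 44.5% | 40.2% / 44.2% | about 0.147 |

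Rises are as common as falls, which is what chance movement looks like.

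**Requiring a significant total effect first.** The total effect is significant in about 76% / 29% of trials. Among those trials the rule fires in 5.3% / 7.3%, 26.5% / 30.0% and 38.3% / 39.4% for the three rows. Per trial, multiply the two:
- unrelated: 0.053 × 0.76 = 4% and 0.073 × 0.29 = 2% (separate runs gave 4–5% / 2%);
- shifted: 0.265 × 0.76 = 20% and 0.300 × 0.29 = 9%;
- fifteen jointly: 0.383 × 0.76 = 29% and 0.394 × 0.29 = 11% (separate run 12%).

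**Sensitivity.** With all 40 approached participants the rates are 5% / 13%, 27% / 36% and 36% / 42%. The correlation was varied from 0.43 (Table 3 footnote, for the secondary outcomes: "SD calculated assuming a correlation of 0.43 between baseline and follow-up measures") to 0.80 (assumed). The unrelated rate is then 6–12% / 16–20%, and the shifted rate 26–33% / 36–40%. The shifted rate falls with sample size: 14% / 28% at n=124 and 1.6% / 13% at n=500.

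**An interval instead.** A 95% percentile bootstrap interval for the indirect effect at n=32 wrongly excludes zero in about 0.1% of trials (unrelated) or 3.5% (shifted).

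**The case against.** The strongest reply is that this is exploratory work, claims only partial mediation, and decides no endpoint. That stands, and it sets the severity. It does not make a pre-set label informative.

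A second reply is that speaking of a relationship being mediated presupposes one, so a significant total effect is implied. The text does not say so, but the reading is fair. A reader might infer from the conditional rates that such a gate would help only with a single unrelated variable. That is wrong: per trial, the gate lowers false labels in all three settings, and at 0.174 W/kg roughly four-fold or more. What remains is that, among trials passing the gate, a shifted but inert variable is still labelled in about 26–31% and fifteen jointly in about 38–40%. A gate alone does not make the label reliable.

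Two other stronger readings are not supported. One is that the plan intends joint entry. It is silent on this, and joint entry would leave only 11 residual degrees of freedom (32 − 6 − 15). The joint rates also assume independent variables, although several listed measures are related. The other is that the rule misfires often whatever the setting. The lowest base-case rate is 8%, and the 1.05 SD shift is planned only for type II fibers.

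Finally, an interval costs sensitivity. That is true, and it is set out under the fix.

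**Conclusion.** The concern holds in qualified form. The rule has no sampling-error component, and its threshold is 0.16 to 0.30 of the standard error at the planned size. With no true mediation it fires in about 8% / 18% of trials for one unrelated variable and about 29% / 38% for one shifted as planned for type II fibers, at true effects of 0.33 / 0.174 W/kg. If about 15 independent variables entered jointly, the figure would be about 40% / 44%.

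These rates assume normal errors. They also assume that the SD of 0.444 and the 12-month correlation of 0.708 apply to the biopsied-leg power measure, which Outcome measures specifies for analyses correlating biopsy findings with power, and to whichever visit is used. Severity is minor: only the mechanistic interpretation is affected.

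**What to change.** Remove the 10% threshold as a label; the percentage change may stay as description. Replace the last sentence of the mediation text with wording such as:

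> We will report the indirect effect (treatment-to-mediator times mediator-to-power), adjusted for baseline, age, gender and race, with a 95% bootstrap confidence interval. Change in percent type II fibers, the substudy primary outcome, is the lead mediator and will be described as evidence of mediation only if the interval excludes zero. Other mediators will be reported with their intervals as hypothesis-generating, without that label.

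Also state whether mediators enter singly or jointly, and which visit's leg power is used. The indirect effect is not divided by the total effect, so it needs no total-effect gate. Restricting the label to one mediator avoids selecting among about 15.

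The cost is SAP wording and a few lines of code, with no new data. The real price is sensitivity. For a mediator shifted 1.05 SD, the interval excludes zero in about 19–22% of trials at an assumed slope of 0.3 and 46–56% at 0.5 (slope in residual SDs of power per mediator SD). The present rule fires in about 82% and 92–97%, but also in 29–38% when the slope is zero. The SAP should say that power for real mediation at n=32 is low, and that the interval does not remove confounding between mediator and power.
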